10.2.3 Reporting and follow up of AEs and SAEs

AE and SAE data will be recorded by the Investigator(s) (or a member of the research team with delegated responsibility to do so) on the Case Report Forms (CRF) and/or SAE report form. Investigators will record all AEs in the AE log in a timely fashion (usually at the time of detection). AEs and SAEs will be followed up until outcome of recovered, recovered with sequelae or death of the study participant.

10.3 Assessment of AEs

Each AE must be assessed for seriousness, causality, severity and expectedness by the Principal Investigator (PI) or another suitably qualified physician in the research team who is trained in recording and reporting AEs and who has been delegated this role. During PI absences appropriately qualified, experienced and trained site staff may assess causality and report SAEs if they have been delegated this responsibility on the delegation log by the PI.

10.3.1 Assessment of Seriousness

The Investigator will make an assessment of seriousness (as defined in section 10.1).

10.3.2 Assessment of Causality

The Investigator will make an assessment of whether the AE is likely to be related to the study intervention according to the following definitions:

- Unrelated: where an event is not considered to have occurred as a result of the study intervention.
- Possibly Related: The nature of the event, the underlying medical condition, concomitant medication or temporal relationship make it possible that the AE has a causal relationship to the study intervention.

Where there are two assessments of causality (e.g. between PI and Chief Investigator (CI)), the causality assessment by the Investigator cannot be downgraded. In the case of a difference of opinion, both assessments are recorded and the 'worst case' assessment is used for reporting purposes.

10.3.3 Assessment of Expectedness

If the AE is judged to be related to the study intervention, the Investigator will make an assessment of expectedness.

- Expected: The type of event is expected in line with the study intervention.
- Unexpected: The type of event was not listed in the protocol or related documents/literature as an expected occurrence.

10.3.4 Assessment of Severity

The Investigator will make an assessment of severity for each AE and this should be recorded on the CRF or SAE form according to the following categories:

- Mild: an event that is easily tolerated by the study participant, causing minimal discomfort and not interfering with every day activities.
- Moderate: an event that is sufficiently discomforting to interfere with normal everyday activities.
- Severe*: an event that prevents normal everyday activities.

*The term 'severe' used to describe the intensity of an event should not be confused with the term 'serious', as defined in section 10.1, which is a regulatory definition based on study participant/event outcome action criteria. For example, a headache may be severe but not serious, while a minor stroke may be serious but is not severe.

10.4 Reporting SAEs to the Sponsor (ACCORD)

Any AE that is assessed as an SAE is subject to expedited reporting requirements to the Sponsor. The SAEs described in 10.2.1 do not require expedited reporting to the sponsor

The Investigator is responsible for reporting SAEs to ACCORD within 24 hours of becoming aware of the event.

SAE reports will either be emailed as a .pdf file to [contact]; or delivered in person using the Serious Adverse Event Report Form. SAE reports will be complete as far as possible and will be signed and dated by the Investigator. The SAE does not require to maintain blinding as this is an unblinded trial. The Research Governance Coordinator, or designee, will complete and return the Cover Sheet and Return Receipt or send an email to confirm receipt of the SAE report within 1 working day. If this email/fax is not received within 1 working day of sending the report to ACCORD, the Investigator must telephone ACCORD on [name] to check that the report has been received by ACCORD.

All copies of SAE reports emailed or faxed to ACCORD and any follow-up information and correspondence will be kept by the Investigator in the Investigator Site File (ISF) and by the Sponsor in the Sponsor File or Trial Master File (TMF).

ACCORD will report SAEs, as required, to the Chief Investigator/Trial Manager within agreed timelines.

11 SUB-STUDY TO EXPLORE REASONS THAT PATIENTS DECLINE CONSENT TO PARTICIPATE (STUDY WITHIN A TRIAL (SWAT))

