10.2 Identifying and Recording AEs and SAEs

10.2.1 AEs and SAEs that do not require reporting

Patients included in the trial will have recently experienced life-threatening illness complicated by multiple events and complications that fulfil the definition of AEs and SAEs. For many patients the risk of further complications and events continues into the post-ICU recovery period. These include, but are not restricted to, events such as new infections, worsening of the original condition causing critical illness, worsening organ failure, critical care readmission, and cardiorespiratory complications.

The judgement of the local research team and PI will determine which events should be reported as AEs and SAEs based on clinical judgement for each event.

The following complications are being collected within the trial, and do not require reporting unless the local research team consider this appropriate:

- Major Adverse Cardiovascular Events (MACE)
- Transfusion Related Adverse Reactions
- Infections
- Death

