10.2.1.1 Assessment of Transfusion Reactions

As mentioned above, transfusion related reactions will be assessed in accordance with the definitions and imputability as set out by SHOT, but will also be recorded as an AE on the trial database. All Serious Transfusion Related Adverse Reactions will be recorded as part of the trial data collection process.

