APPENDIX 1 – Expected Transfusion Reactions as defined by SHOT

CATEGORY	TERM				
	IBCT-WCT	Incorrect blood component transfused – Wrong Component Transfused			
ADVERSE REACTIONS	IBCT-SRNM	Incorrect blood component transfused – Specific Requirements Not Met			
	ADU	Avoidable transfusion, Delayed transfusion or Under- or Over-transfusion			
	HSE	Handling and storage errors			
	RBRP	Right blood Right Patient			
	Near Miss				
	FAHR	Febrile, allergic and hypotensive reactions (formerly known as acute transfusion reactions)			
	HTR Acute				
	HTR Delayed	Haemolytic Transfusion Reaction			
SERIOUS ADVERSE	PTP	Post-transfusion purpura			
REACTIONS	TA-GvHD	Transfusion Associated graft versus host disease			
	TACO	Transfusion associated circulatory overload			
	TAD	Transfusion associated dyspnoea			
	TRALI	Transfusion related acute lung injury			
	TTI	Transfusion transmitted infection			
OTHER REPORTING	Anti-D				
CATEGORIES	Cell Salvage				

Full definitions of terms can be found at:

https://www.shotuk.org/wp-content/uploads/myimages/SHOT-Definitions-update-10.01.20-FINAL.pdf

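### Sections 10.2.1 and 10.4 exempt transfusion reactions, deaths, MACE and infections from expedited sponsor reporting by event type, with no exception for events judged related to the study transfusion

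*Protocol*

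**What the plan says.** Section 10.4 opens with a general rule: "Any AE that is assessed as an SAE is subject to expedited reporting requirements to the Sponsor". The investigator has 24 hours from becoming aware of the event. The next sentence creates an exemption: "The SAEs described in 10.2.1 do not require expedited reporting to the sponsor".

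Section 10.2.1 is headed "AEs and SAEs that do not require reporting". It explains that these patients have just survived life-threatening illness and remain at risk of further complications. It then lists four categories that are already collected as trial data: MACE, "Transfusion Related Adverse Reactions", infections and death. These do not "require reporting unless the local research team consider this appropriate".

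Section 10.2.1.1 has transfusion reactions graded by SHOT definition and imputability, "but will also be recorded as an AE on the trial database". Serious ones are also captured as trial data.

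Four other sections bear on the point:
- 10.1.3 defines a transfusion related reaction as an unwanted response to the blood component given.
- 10.1.4 makes such a reaction serious if, among other criteria, it is fatal or life-threatening.
- 10.2.2 limits AE and SAE reporting to the time from randomisation to hospital discharge.
- 10.3.2 has the investigator grade each AE as unrelated or possibly related to the study intervention.

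**The concern.** Exempting common complications from expedited reporting is reasonable in a population with high background morbidity, provided they are collected as outcomes. The reason given in 10.2.1 is that background risk: infections, worsening illness or organ failure, readmission to critical care, cardiorespiratory events. It does not extend to a transfusion reaction, which arises from the treatment under test.

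The trial gives one arm extra transfusions and has their safety as a secondary objective (section 2.2). A serious reaction to a study transfusion, or a death judged possibly related to one, is the kind of event a sponsor would want to hear of at once. Under 10.4 it has no required prompt route. Whether it is reported depends on local teams in an unblinded trial, who are given no criterion, so sites may handle identical events differently.

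**Working it through.** No figure in the protocol depends on this point, so the check sets the provisions side by side.

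1. **Scope.** I take the SAEs exempted by 10.4 to be those in the 10.2.1 list. The heading of 10.2.1 names SAEs as well as AEs, so serious events in the four categories are included.

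2. **Is there a condition on relatedness?** None appears in 10.2.1 or 10.4. Section 10.3.2 does say that, when two causality assessments differ, the worse is used for reporting. For an exempt category 10.4 applies no causality test, so that rule has nothing to act on.

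3. **Is relatedness built into any category?** Yes, into one. By 10.1.3 a transfusion related reaction is a response to the transfused component. In the intervention arm, transfusions given under the allocation are the study intervention (section 6.1.2.3).

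4. **What must reach the sponsor, and when?**

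| Event | Required notice to sponsor | Stated deadline | Section |
|---|---|---|---|
| SAE outside the four categories | Yes | 24 hours | 10.4 |
| Serious transfusion related reaction | No; local option | None | 10.2.1, 10.4 |
| Serious MACE, infection or death, possibly related | No; local option | None | 10.2.1, 10.4 |
| Serious MACE, infection or death, unrelated | No; local option | None | 10.2.1, 10.4 |
| Patient randomised in error (violation) | Yes | 3 days | 13.4.1.2, 13.4.1.3 |
| Transfusion deviation (log) | Yes | Every 2 months | 13.4.1.3 |

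The third and fourth rows are identical, so the causality assessment changes nothing for these categories. The second row shows that a fatal transfusion reaction carries no stated deadline, whereas a randomisation error does.

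5. **Is the event lost?** No. Section 10.2.1.1 puts reactions on the trial database as AEs. Section 10.2.3 asks for AEs to be logged in a timely way, usually when detected. Sections 2.3.2 and 7.3 and Table 1 collect the four categories as outcomes. What is missing is mandatory notice to the sponsor within 24 hours.

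**The case against.** The strongest reply is that the exemption is deliberate and explained. All four categories are collected, reactions receive SHOT grading, each AE is assessed for seriousness, causality, severity and expectedness (10.3), the local team may report any event, and a DMC oversees safety (12.6). Section 10 places reporting under SOP CR006. Neither that SOP nor the DMC charter is shown, so another route to the sponsor or the DMC cannot be excluded. All of this stands. It limits the point to prompt, mandatory notification and lowers confidence that no route exists. It does not remove the point: 10.4 is the instruction that sites follow, it states the exemption without a relatedness condition, and it cites no other route.

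A reader might infer more, and the protocol does not support it:

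- **That 10.2.1 and 10.2.1.1 contradict each other.** Recording a reaction as an AE on the database and reporting it to the sponsor are different acts, so the two sections are compatible.
- **That the expectedness rules make matters worse.** Section 10.3.3 calls an event unexpected only if "The type of event was not listed in the protocol or related documents/literature as an expected occurrence", and Appendix 1, titled "Expected Transfusion Reactions as defined by SHOT", is broad. But 10.4 does not make reporting depend on expectedness. A narrower Appendix 1 would change no reporting duty shown in this protocol.
- **That deaths in general are harms of the intervention.** Nothing shows this, and background risk is a fair reason to exempt unrelated deaths. The concern is confined to those judged at least possibly related.

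**Conclusion.** The concern holds in a limited form. By event type alone, 10.2.1 and 10.4 remove the mandatory 24-hour sponsor report for all four categories. One of these is related to transfusion by definition, and none has an exception for related events. The protocol should be changed, but the point is one of safety oversight and does not touch the primary analysis.

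The number of events affected cannot be estimated from the document, which gives neither units transfused per patient nor a reaction rate. It is tempting to scale the deaths in section 9.1: 12/182 = 6.6%, and 346 × 12/182 = 22.8, or about 23. That would mislead. Those deaths occurred during follow-up, SAE reporting ends at hospital discharge (10.2.2), and the count does not separate related from unrelated deaths.

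The conclusion assumes that 10.4 means what it says, and that neither CR006 nor the DMC charter already requires prompt notice of these events.

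**What to change.** Amend 10.2.1 and 10.4 as follows:

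- Limit the exemption to events in the listed categories that are assessed as unrelated to study transfusion.
- Send every serious transfusion related reaction to the sponsor within 24 hours by the existing SAE route.
- Do the same for every serious MACE, infection or death assessed under 10.3.2 as at least possibly related.
- Remove the local-discretion clause for these events. It can stay for unrelated ones.
- If CR006 or the DMC charter already provides a prompt route, cite it in 10.4.

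Sections 10.2.1.1 and 10.3.3 and Appendix 1 need no change on this account. The cost is a protocol wording amendment and a small number of extra SAE forms during the intervention period, using a form and deadline that sites already have.

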11.1 Context

The optimum methodology for post-ICU intervention trials such as ABC is uncertain, but enrolment and inclusion bias are a concern given the wide variation in patient demographics, critical illness aetiology, and critical illness type/severity/duration. In previous trials, rates of consent among patients approached have been relatively low at around 30-50%. This seems surprising given the trials are generally framed

around comparing usual care to an intervention designed to test a hypothesis for improved recovery.

The reasons for low agreement to participate from a patient and participant perspective have not been explored in a UK setting. It is likely that there are various decision-making processes involved when patients are approached to participate in a post-ICU intervention trial such as this. These may relate to the organisation, for example, resource allocation and the provision of trial-related documentation. The chain of determining eligibility, inviting patients to participate, and gaining consent may also be influenced by participant-related factors. These may include staff and patients' attitudes towards the study, professional role and style, and the perceived and actual health status of the patient. Considerations of equality, diversity, and inclusion (EDI) are also important, to ensure that all people can potentially take part in research. Ensuring EDI are maximised will also increase the generalisability and relevance of the research. Understanding these issues in more detail is important for future research into ICU recovery, to avoid inclusion bias, and ensure patients with a wide range of socio-economic, health, and other characteristics are included.

11.2 Research Questions

Our overarching research question is: 'Among patients who are screened as being eligible for the trial and are approached for consent by the research team, what are the reasons that patients decline participation?'

We will aim to answer the following specific research questions:

- 1. What are the reasons that eligible patients are not approached for consent to the trial?
- 2. What are organisational factors that contribute to declining participation in the trial (e.g. local resources, professional role/grade of person seeking consent, experience of researcher)?
- 3. What are the patient/participant related factors that contribute to declining participation in the trial (e.g., demographic, ICU illness type or severity, cognitive status/capacity, fatigue)?
- 4. How does the information provided (written, visual, verbal) impact on the consent process?
- 5. Are there other contextual factors that impact on the consent process (e.g., family involvement, timing of approach during recruitment window, parent clinical teams, local research culture/practices)?

[figure not shown]
11.3 Logic Model

A proposed logic model underpinning the reasons that eligible patients may not consent to participate in the trial is shown in figure 2. This model will underpin the proposed surveys, interviews, and focus groups and will be modified according to emerging data.

Figure 2: Preliminary logic model for reasons that eligible patients do not participate in the ABC post-ICU trial

ABC CONSENT PATHWAY LOGIC MODEL

11.4 Methodology

This mixed methods SWAT will comprise 5 parts:

- 1. PPI focus groups will be conducted with a group of previous ICU patients and their relatives to seek their views on why people may decline participation at this period of their recovery. These will seek to include people representing relevant issues and characteristics highlighted in the NIHR EDI toolkit. This work will be conducted with the Lothian critical care PPI volunteer group, and may inform the survey design and interview guides. No patients participating in the trial will be involved in these focus groups.
- 2. Recruitment data from screening logs will be summarised to aid purposive sampling of sites for part 3 and ensure a maximum variation sample.
- 3. A survey will be developed on the REDCap platform, that will ask research staff to rate the importance of different factors based on their experience of approaching patients in the trial. This will be developed by the research team. This will involve as many research staff as possible across all participating sites (approximately 30-40 individuals).
- 4. Up to 15 semi-structured interviews will be conducted at a purposive sample of sites with research staff who have been approaching patients for consent in the trial, across the participating ICUs. Additional interviews will be considered if data saturation is not achieved. We will use the 'logic model' (a simple visual plan showing resources and activities involved in the consent process) to hypothesise all the possible reasons people may decline to participate. The logic model will be used to guide the interviews which will explore the key reasons people seem to decline. This will include consideration of the aspects of inclusion highlighted in the NIHR Equality, Diversity and Inclusion Toolkit (EDI Toolkit (rssleicesterresources.org.uk)
- 5. We will summarise the baseline characteristics of patients who agreed to participate in the trial, and seek published or otherwise available comparator populations of anaemic ICU survivors to explore whether these are representative of all ICU patients, or whether important differences exist.

The demographics, job role and experience of participants will be recorded, together with information about their involvement in the ABC Post ICU trial (duration, patients approached and recruited etc). The PPI group discussions will be captured using note-taking and examining materials produced such as charts and 'post-it' notes (part 1, above). The semi-structured interviews with research staff (part 4, above) will be audio-recorded and transcribed verbatim. Interviews will be digitally recorded using an approved device, and transcribed verbatim by an approved transcribing service for the University of Edinburgh. Audio files will be saved within the secure project folder prior to being downloaded for transcription. Once the transcript is checked, the audio file will be deleted. The interview transcripts will then be analysed using an inductive framework analysis approach. This approach is ideal for analysing text and leaves a clear audit trail from the raw data to the final themes (including illustrative quotes). The framework method is the most suitable approach for this analysis as the aim is to use the data to explore participants' experiences and describe and interpret what happens in a particular setting systematically and transparently. The findings from all 5 parts will then be integrated to summarise and explain the main reasons and issues that mean ICU survivors declined to participate in the trial. A specific

focus of interest will be factors that are specific to this trial versus factors that may be more generic in relation to participation in ICU recovery trials.

11.5 Outputs

The results of the sub-study will be reported separately in presentations and a publication.

12 OVERSIGHT ARRANGEMENTS

12.1 INSPECTION OF RECORDS

Investigators and institutions involved in the study will permit trial related monitoring and audits on behalf of the sponsor, REC review, and regulatory inspection(s). In the event of audit or monitoring, the Investigator agrees to allow the representatives of the sponsor direct access to all study records and source documentation. In the event of regulatory inspection, the Investigator agrees to allow inspectors direct access to all study records and source documentation.

12.2 STUDY MONITORING AND AUDIT

The ACCORD Sponsor Representative will assess the study to determine if an independent risk assessment is required. If required, the independent risk assessment will be carried out by the ACCORD Quality Assurance Group to determine if an audit should be performed before/during/after the study and, if so, at what frequency.

Risk assessment, if required, will determine if audit by the ACCORD QA group is required. Should audit be required, details will be captured in an audit plan. Audit of Investigator sites, study management activities and study collaborative units, facilities and 3rd parties may be performed.

12.3 PUBLIC ENGAGEMENT

A patient Personal and Public Involvement (PPI) representative will act as coinvestigator throughout the trial to ensure the views and opinions of service users, carers and the public are represented. In addition, a wider PPI group will be consulted on the protocol prior to submission for ethical approval, and specifically will be asked to review patient and patient-representative materials including the Patient (or representative) Information Leaflet and consent forms.

The views of PPI representatives will be sought during interpretation of the study results as appropriate.

12.4 TRIAL MANAGEMENT GROUP

The trial will be coordinated by a Project Management Group, consisting of selected grant holders, a trial manager and trial nurse.

The Trial Manager will oversee the study and will be accountable to the Chief Investigator. The Trial Manager will be responsible for checking the CRFs for completeness, plausibility and consistency. Any queries will be resolved by the Investigator or delegated member of the trial team.

A Delegation Log will be prepared for each site, detailing the responsibilities of each member of staff working on the trial.

